15.4.2. Coding Dictionaries

Concomitant medications entered into the database will be coded using the WHO Drug Reference List, which employs the Anatomical Therapeutic Chemical classification system. Coexistent diseases and AEs will be coded using the Medical Dictionary for Regulatory Activities (MedDRA).

A complete description of data to be collected is provided in the trial documentation.

15.4.3. Data Handling

Data will be entered in a timely manner and in accordance with a trial management plan.

15.4.4. Direct Access to Source Data/Documents

The investigator/trial site is to provide direct access to source data/documents for trial-related monitoring, audits, IRB/HREC/IEC review, and regulatory inspection.

15.4.5. Record Keeping

The investigator is responsible for maintaining adequate records to fully document the conduct of the trial consistent with that noted in ICH E6, including but not limited to the following:

1. All versions of the Investigator's Brochure
2. Signed Protocol and Amendments in effect during the conduct of the trial
3. Signed ICFs
4. Source documents, including adequate case histories, questionnaires, and subject diaries
5. Signed, dated, and completed eCRFs and documentation of data corrections
6. Notification of SAEs and related reports
7. Dated and documented IRB/HREC/IEC approvals and approval by regulatory authorities, as required
8. Normal laboratory reference ranges
9. Laboratory certifications
10. Curricula Vitae of all clinical investigators
11. Completed Forms FDA 1572
12. SIV documentation
13. Delegation of Authority Log
14. Subject Screening & Enrollment Log(s), Subject Identification Code List
15. Investigational product accountability documentation
16. Signed agreements between involved parties
17. Relevant communication, including that related to monitor site visits (eg, letters, meeting notes, notes from telephone calls)
18. Interim, annual, or final reports to IRBs/HREC/IEC and regulatory authorities, as required
19. Audit certificate(s), if applicable

15.5. DATA QUALITY CONTROL

15.5.1. Monitoring Procedures

The Sponsor and/or its representative may make periodic visits to the investigational site to assess compliance with trial procedures and regulatory requirements; to ensure that the safety, welfare, and privacy of subjects are being protected; and to verify the accuracy and integrity of the trial data. In addition, independent Quality Assurance site audits may be conducted as verification of the quality and compliance of trial conduct.

The Sponsor and/or its representative will periodically review the trial data to ensure that data are being appropriately collected and reported. Queries and corrections will be made as needed.

15.5.2. Data Management

Sponsor or designee will be responsible for activities associated with the data management of this trial. The standard procedures for handling and processing records will be followed per GCP and Contract Research Organization (CRO)'s standard operating procedures (SOPs). A comprehensive data management plan (DMP) will be developed including a data management overview, description of database contents, annotated eCRFs, user acceptance testing procedures, query contacts, and consistency checks.

Trial site personnel will be responsible for providing resolutions to all data queries. The investigator will be required to document electronic data review to ensure the accuracy of the corrected and/or clarified data. Procedures for soliciting and documenting resolution to data queries are described in the trial manual.

15.6. AUDITING PROCEDURES

In addition to the routine monitoring procedures, a GCP Quality Assurance audit may be initiated by the Sponsor. The investigator has to ensure that subjects/parents/legal guardians are aware of and consent to personal information being reviewed during the data verification process as a part of monitoring/auditing/inspection by the Sponsor, properly authorized agents of the Sponsor, or competent authorities. In addition, participation and personal information is treated as strictly confidential to the extent that applicable law permits and to which it is not publicly available. The purpose of audits and inspections is to evaluate compliance with the principles of GCP, international and local regulatory requirements, and the trial protocol. The audit or inspection may include, for example, a review of all source documents, drug records, original clinic medical notes, and some or all of the facilities used in the trial.

The audits may be conducted by the Sponsor or Sponsor's selected agent in accordance with Sponsor's SOP or SOPs of the selected and properly authorized agent. A competent authority may also wish to conduct an inspection during the trial or after its completion. If an inspection is requested by a competent authority, the investigator must inform the Sponsor immediately that this request has been made. The investigator and his/her institution will permit all monitoring, audits, and regulatory inspections, providing direct access to source data.

15.7. LABORATORY QUALITY STANDARDS

Laboratory tests or evaluations described in this protocol will be conducted in accordance with quality laboratory standards as described in the SOPs of the central laboratories. Some serum or plasma samples may be used for bioanalytic test validation.

The laboratories will provide a list of reference ranges for applicable analyses before trial start. These will be held in the investigator site file and the trial master file. The methods employed for each assay should be available on request. Any change in the laboratory procedures, reference values, etc., during the trial must promptly be communicated to the Sponsor. The laboratories may also be audited by the Sponsor or by competent authorities.

15.8. TRIAL TERMINATION OR COMPLETION

The investigator should notify the IRB/HREC/IEC in writing of the completion or early termination of the trial. Upon trial completion or termination, applicable regulatory reporting requirements will be followed. The Sponsor reserves the right to terminate the trial at any time for any reason.

15.9. CHANGES TO THE PROTOCOL

Changes in any portion of this protocol must be documented in the form of an amendment from the Sponsor and must be approved by the investigational site's IRB/HREC/IEC and regulatory authorities, as required, before the amendment is implemented. However, in the event of apparent immediate hazard to a subject, a deviation from the protocol is allowed to eliminate the hazard. In this case, the deviation and the reason for it must be submitted for approval as required by regional regulations to the applicable IRB/HREC/IEC and regulatory authorities, along with a proposed protocol amendment if appropriate.

Protocol amendments may only be made with prior written approval of the Sponsor and/or its representative and documented approval or favorable opinion from applicable regulatory authorities or regional IRB/HREC/IEC, as required. The investigator must send a copy of the documented approval to the Sponsor and/or its representative.

15.10. OTHER CHANGES IN TRIAL CONDUCT

Changes in trial conduct are not permitted. Any unforeseen changes in trial conduct will be recorded in the clinical study report.

15.11. USE OF INFORMATION AND PUBLICATION

The data and information generated in this trial are the exclusive property of the Sponsor and are confidential. Written approval from the Sponsor is required prior to disclosing any information related to this trial. Publication of the results will be based on appropriate analyses and review of the complete data. Authorship will be determined based on enrollment of eligible subjects or contribution to the design, conduct, or interpretation of the trial. Publication of any data of this trial without prior Sponsor approval is not permitted.

16. ETHICAL AND LEGAL CONSIDERATIONS

This trial will be conducted in accordance with the following:

- Protocol-related and trial-related documents
- GCPs as outlined in ICH E6 and regional regulations
- Declaration of Helsinki
- Regional required subject data protection laws and regulations
- Applicable regional regulations

16.1. INDEPENDENT SAFETY COMMITTEE

Independent oversight of this trial will be provided by an ISC. Its duty is to regularly review the progress of the trial and assess accumulating safety data. After each meeting, it will advise the Sponsor on the continuing safety of current trial subjects and on the continuing validity and scientific merit of the trial. All decisions about the conduct of the trial will rest solely with the Sponsor. The ISC will consist of at least 1 pediatric endocrinologist and 1 physician of another relevant medical discipline, all with experience in clinical studies, who will operate based on the ISC Charter agreed to by all ISC members. The Charter will define data content and review frequency.

The Sponsor may attend the ISC meetings.

The ISC is empowered to recommend the following courses of action with respect to continuing the trial:

1. the trial should continue without modification
2. the trial should continue but with modification to the protocol, or with additional data presentation needed
3. trial enrollment and treatment administration should be temporarily suspended pending further data evaluation, or
4. the trial should be terminated because of safety concern

The responsibility for the final decision regarding the ISC-recommended course of action will rest with the Sponsor.

16.2. INFORMED CONSENT

The draft ICF must be reviewed by the Sponsor and/or its representative prior to submission to a regional IRB/HREC/IEC for approval. A copy of the ICF approved by the review board must be forwarded to the Sponsor and/or its representative.

The ICF (and subject information sheet, if applicable) documents the trial-specific information the investigator provides to the subject and the subject's agreement to participate. The investigator or designee will fully explain in layman's terms the nature of the trial along with the aims, methods, anticipated benefits, potential risks, and any discomfort participation may entail. The ICF and subject information sheet must be appropriately signed and dated before the subject undergoes any trial-related procedure. The original and any amended signed and dated ICFs and subject information sheets must be retained at the trial site with a copy of each provided to the subject.

16.3. IRB/HREC/IEC APPROVALS

The Principal Investigator at each site is responsible for obtaining approval from the appropriate regional IRB/HREC/IEC for the final protocol, Sponsor-approved ICF and subject information sheet (if applicable), and any advertisements to recruit subjects. Written approval of these documents must be obtained from the committee before any subject is enrolled at a trial site.

The Principal Investigator is also responsible for the following interactions with the regional IRB/HREC/IEC:

1. Obtaining review board approval for any protocol amendments and ICF revisions before implementing the changes
2. Providing the review board with any required information before or during the trial
3. Submitting progress reports to the review board as required during the conduct of the trial, requesting re-review and approval of the trial as needed, and providing copies of all review board re-approvals and relevant communication to the Sponsor and/or its representative
4. Notifying the review board of all serious and unexpected AEs related to the investigational product reported by the Sponsor and/or its representative, as required
5. Notifying the review board of the end of trial participation, in accordance with regional guidelines and regulations

16.4. SUBJECT COMPENSATION FOR ADVERSE EFFECTS ON HEALTH

The Sponsor and/or its representative will adhere to regional regulations regarding clinical trial compensation of subjects whose health is adversely affected by taking part in the trial.

16.5. FINANCE AND INSURANCE

Will be described in trial documents.

18.2. SCHEDULE OF EVENTS

	VISIT 1 ¹	VISIT 2	VISIT 3	VISIT 4	VISIT 5/CV/ETV ²
	Week 1 Day 1	Week 13 (± 2 weeks)	Week 26 (± 2 weeks)	Week 39 (± 2 weeks)	Week 52 (± 2 weeks)
	Morning	5d ± 1d Post-Dose, Morning	5d ± 1d Post-Dose, Morning	5d ± 1d Post-Dose, Morning	5d ± 1d Post-Dose, Morning
Informed consent	x				
Interval history, medications and health status review ³	x				
Vital signs measurements ⁴	x	x	x	x	x
Height ⁵ & weight	x	x	x	x	x
Physical examination	x	x	x	x	x
Pubertal status assessment	x	x	x	x	x
Blood sample collection – A ⁶	x	x	x	x	x
Blood sample collection – B ⁷	x		x		x
Bone age x-ray ⁸	x				x
Investigational product preparation/administration training	x				
Training on GH Auto-Injector ⁹	(x)	(x)	(x)	(x)	(x)
Subject diary training	x				
C&OS-P ¹¹	x ¹⁰	x			
CSDS-P ¹¹	x ¹⁰	x			
CSDS-C ^{11,12}	x ¹⁰	x			
PQ-P ¹¹		x			
PQ-C ^{11,12}		x			
DUQ ¹¹		x			
Investigational product dose adjustment ¹³	x	x	x	x	x
Local tolerability assessment ¹⁴	x	x	x	x	x
Investigational product & subject diary dispensing	x	x	x	x	x
Investigational product compliance ¹⁵		x	x	x	x
Concomitant medications		x	x	x	x
Adverse events ¹⁶		x	x	x	x

- ¹ Visit 1 of this extension trial should be the same day as the final visit of the prior trial, and the first dose should occur as soon as possible. A period of up to approximately 6 weeks between the final visit of the prior trial and first dose (Day 1) of the extension trial is acceptable. Visit 1 assessments should be performed unless they were performed for the final visit of the prior trial. In the unusual event there is a gap of 4 to approximately 6 weeks, then all Visit 1 assessments should be repeated for Day 1 except physical exam, blood collection and bone age x-ray.
- ² After Visit 5, visits continue every 3 months (See Section 10.2.2.3 and Section 10.2.2.5). A Completion Visit (CV)/Early Termination Visit (ETV) should be performed for all subjects either completing the trial as described in Section 10.1, or terminating trial participation prematurely. The visit should include all procedures listed for Visit 5, as applicable.
- ³ Medications and health status: Interval history only to be recorded in case of new disease states since the last visit of the prior trial; disease states diagnosed since the initiation of the prior trial (eg, new onset migraines) are medical history; Medical history from the prior trial will be carried forward into this trial's database; Ongoing AEs from the prior trial will be followed until resolution or stabilization; Review of subject diary from the prior trial; Current therapies.
- ⁴ Vital sign measurements include heart rate, blood pressure, respiratory rate and body temperature, which should be performed after the subject has rested for at least 5 minutes.
- ⁵ Height should be measured at each visit at approximately the same time of day, preferably by the same auxologist.
- ⁶ Blood sample collection – A includes IGF-1, IGFBP-3, antibodies against hGH and PEG, and for females of child-bearing potential hCG. If warranted, TransCon hGH, hGH, and PEG serum levels may be analyzed for the interpretation of immunogenicity titers
- ⁷ Blood sample collection – B includes mPEG, hormone/glycemic status (TSH, FT4, FT3, morning cortisol, and HbA1c), chemistry, hematology, and lipid panel. Fasting not required.
- ⁸ Bone age x-ray may not be required at Visit 1 if there is documentation of a bone age x-ray performed within the past 52 weeks. However, if subject's prior documented bone age was > 12.0 years, and it was performed greater than 9 months prior to Visit 1, a bone age x-ray should be performed within approximately 4 weeks of Visit 1. Bone age x-ray may also be performed at any time, if clinically indicated.
- ⁹ Once the GH Auto-Injector is available, transition to the GH Auto-Injector will occur in the US (only) at the next regularly scheduled trial visit when thorough training on preparation and administration will occur.
- ¹⁰ At Visit 1, the C&OS-P, CSDS-P, and CSDS-C should be completed for all subjects.
- ¹¹ For subjects who were treated with Genotropin in the prior TransCon hGH CT-301 trial, C&OS-P, CSDS-P, CSDS-C, PQ-P, and PQ-C will be completed (as applicable) within the subject diary immediately prior to the 6th dose of investigational product, and in clinic at Visit 2, prior to review of the subject diary, AEs, and concomitant medications. For subjects transitioning to the GH Auto-Injector, C&OS-P, CSDS-P, and CSDS-C will be completed (as applicable) within the subject diary immediately prior to the 6th dose after transition to the GH Auto-Injector, and again in clinic at the following scheduled visit, prior to review of the subject diary, AEs, and concomitant medications. Additionally, for subjects transitioning to the GH Auto-Injector, the DUQ will be completed within the subject diary on the day of the 6th dose of investigational product, and in clinic at Visit 2, prior to review of the subject diary, AEs, and concomitant medications.
- ¹² CSDS-C and PQ-C should only be completed by subjects \geq 9 years old at the time of Visit 1, and/or at the transition to the GH Auto-Injector, as applicable.
- ¹³ Dose adjustments at visits are typically based on subject weight at visits. However, dose adjustments may occur between visits per Section 9.6.
- ¹⁴ Local tolerability assessment at the injection site to be performed at time of injection, and by the trial staff at visits.
- ¹⁵ Investigational product compliance includes review of subject diary and returned investigational product.
- ¹⁶ AE review includes review of subject diary and physical examination of injection sites. AEs that are considered mild and not related to investigational product will not be reported on the AE CRF. AEs reported up to 14 days after the final dose of TransCon hGH will be captured.

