- Preference Questionnaire – Child (PQ-C): **only for subjects \geq 9 years old (at Visit 1)**
- C&OS-P
- CSDS-P
- CSDS-C: **only for subjects \geq 9 years old (at Visit 1)**

Note: The questionnaires to be taken before the 6th investigational product administration will be in the subject diary. At Visit 2, the questionnaires are to be completed at the clinic visit, prior to review of the subject diary, adverse events (AEs), and concomitant medications.

For all subjects who have transitioned to the GH Auto-Injector:

Immediately prior to the 6th investigational product administration using the GH Auto-Injector, and at the next scheduled clinic visit (approximately 13 weeks after transition to the GH Auto-Injector), the following patient-reported outcome questionnaires will be completed by subjects/parents/legal guardians/caregiver, as applicable.

- C&OS-P
- CSDS-P
- CSDS-C **only for subjects \geq 9 years old at transition to GH Auto-Injector**

On the day of the 6th investigational product administration using the GH Auto-Injector (either immediately before or after the injection), and at the next scheduled clinic visit (approximately 13 weeks after transition to the GH Auto-Injector), the following questionnaire will be completed by the individual primarily preparing and performing the injection with the GH Auto-Injector.

- Device Usability Questionnaire (DUQ)

Note: The subject diary will include the questionnaires to be taken immediately before the 6th investigational product administration, and on the day of the 6th investigational product administration using the GH Auto-Injector. At the next scheduled visit (approximately 13 weeks after transition to the GH Auto-Injector), the questionnaires will be completed at the clinic visit, prior to review of the subject diary, AEs, and concomitant medications.

Ongoing Visits:

Visit 2 and subsequent scheduled visits every 13 weeks (\pm 2 weeks) will be performed 5 days (\pm 1 day) post-dose. The following will be performed:

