7. Pubertal status assessment (Tanner stage)
8. Blood collection for the following laboratory assessments*:
 - IGF-1 and IGFBP-3
 - Antibodies against hGH and PEG
 - If warranted, TransCon hGH, hGH, and PEG serum levels may be analyzed for the interpretation of immunogenicity titers
 - mPEG

- Hormone/glycemic Status (TSH, FT4, FT3, morning cortisol, and HbA1c)
- Chemistry
- Hematology
- Lipid panel
- **Females of child-bearing potential only:** hCG
*Fasting not required. Banked blood samples may be used for additional characterization of anti-drug antibody responses.

9. Investigational product dose adjustment, as needed

10. Investigational product & subject diary dispensing

An overview of all visits is provided in the Schedule of Events, Section 18.2.

10.2.2.4. Patient-Reported Outcome Completion (6th week after transition to the GH Auto-Injector) and Device Usability Questionnaire

For all subjects who have transitioned to the GH Auto-Injector (6th week of GH Auto-Injector Use): Immediately prior to the 6th dose of the GH Auto-Injector, and at the next scheduled clinic visit (approximately 13 weeks after transition to the GH Auto-Injector), patient-reported outcomes questionnaires will be completed by subjects/parents/legal guardians/caregivers, as applicable. At 6 weeks after transition to the GH Auto-Injector, the questionnaires will be completed in the subject diary. At the next scheduled clinic visit (approximately 13 weeks after transition to the GH Auto-Injector), the questionnaires will be completed at the clinic visit, prior to review of the subject diary, AEs, and concomitant medications. The questionnaires are:

- C&OS-P
- CSDS-P
- **CSDS-C: only for subjects ≥ 9 years old (at time of transition to GH Auto-Injector)**

In addition, on the day of the 6th dose using the GH Auto-Injector (either immediately before or after the 6th dose) and at the next scheduled clinic visit (approximately 13 weeks after transition to GH Auto-Injector), the following questionnaire will be completed by the individual primarily responsible for preparing and performing the injection with the GH Auto-Injector.

- DUQ

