11.7.4. Device Usability Questionnaire

The Device Usability Questionnaire will be administered during this trial to assess GH Auto-Injector comfort, ease-of-use, and safety from the point of view of the caregivers and subjects. The data will supplement the GH Auto-Injector ease-of-use and functionality data gathered from a previous phase 1 clinical trial (comparing TransCon hGH administered by GH Auto-Injector and by syringe/needle), as well as data gathered during the formative and summative usability studies conducted in the device design and development phases. The data will also be analyzed as part of this current trial's overall assessment of safety and efficacy.

The DUQ was designed for use by children and/or adults. It consists of eight statements that the subject or caregiver (ie, whomever is designated as the individual primarily responsible for preparing and performing the injection with the GH Auto-Injector) is asked to rank on a scale indicating level of agreement. The statements relate to the level of comfort, ease-of-use, and safety.

This timing of DUQ administration is outlined in Section 10.2.2.4.

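### The Schedule of Events times the Device Usability Questionnaire from the start of the trial, whereas the synopsis and Section 10.2.2.4 time it from the switch to the GH Auto-Injector

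*Protocol*

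**What the plan says.** **Schedule of Events, Section 18.2.** The DUQ row has one mark, under Visit 2 (Week 13 ± 2 weeks). Note 11 limits the DUQ to subjects transitioning to the device and then gives the timing: "the DUQ will be completed within the subject diary on the day of the 6th dose of investigational product, and in clinic at Visit 2".

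**The same note, other questionnaires.** For the same device switchers, C&OS-P, CSDS-P and CSDS-C fall "immediately prior to the 6th dose after transition to the GH Auto-Injector, and again in clinic at the following scheduled visit". For subjects who took Genotropin in CT-301, the questionnaires fall "within the subject diary immediately prior to the 6th dose of investigational product, and in clinic at Visit 2".

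**Text on the DUQ elsewhere in the protocol.** The synopsis sets the diary DUQ as follows: "On the day of the 6th investigational product administration using the GH Auto-Injector". Section 10.2.1, item 9, also counts the sixth dose taken with the device when it describes the diary reminder. Section 10.2.2.4 gives the same diary timing as the synopsis and adds the clinic time point: "at the next scheduled clinic visit (approximately 13 weeks after transition to GH Auto-Injector), the following questionnaire will be completed". Section 11.7.4 states: "This timing of DUQ administration is outlined in Section 10.2.2.4". The form in Appendix 6 has a header field for the week after transition.

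**When the switch happens.** Schedule note 9: "transition to the GH Auto-Injector will occur in the US (only) at the next regularly scheduled trial visit". The device training row carries a conditional mark at each of Visits 1 to 5. Under Section 9.3, children below the Table 2 weight ranges stay on syringe and needle until they reach one.

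**The concern.** The DUQ asks about pain, mistakes, skin marks and injury with the device, which nobody can answer before using it. The Schedule fixes both time points relative to trial entry, but the switch can fall at any regular visit. A site that followed the Schedule for a late switcher would either hand out the form too early or, once Visit 2 had passed, find no time point left at which to collect it. A missed response at six or thirteen weeks of device use cannot be recovered afterwards.

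Comfort, ease of use and safety of the device form a secondary objective (Section 6.2), and the DUQ is the only questionnaire specific to the device. The SAP does not settle the timing. Its schedule has no DUQ row, its Section 11.4 states no DUQ time point, and its analysis windows (Table 2) count from the extension study day, not from the switch.

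**Working it through.** No power or sample-size figure is involved. The check is a dose and visit calendar.

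**Inputs**
- Weekly dosing, with dose 1 on Day 1: dose *k* falls on day 1 + 7(*k* − 1).
- Protocol Section 10.2: Visit 2 is 5 days (± 1) after the 11th to 15th dose, nominally the 13th. Visit 3 is 5 days after the 26th dose, and the pattern continues, so Visit *v* is nominally 5 days after dose 13(*v* − 1).
- Assumption: a subject trained at Visit *v* (from Visit 2 on) first uses the device at the next weekly dose, *f* = 13(*v* − 1) + 1. For a switch at Visit 1, *f* = 1.

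**Calendar check against the SAP.** Visit 2 = 1 + 7 × 12 + 5 = day 90, and Visit 3 = 1 + 7 × 25 + 5 = day 181. Both equal the target days in SAP Table 2.

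**Formulas.** Device doses taken by trial dose *n* = max(0, *n* − *f* + 1). Sixth device dose = trial dose *f* + 5.

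| Switch at | First device dose | Schedule: device doses by trial dose 6 (day 36) | Schedule: device doses by Visit 2 (day 90) | Section 10.2.2.4: sixth device dose | Section 10.2.2.4: clinic DUQ |
|---|---|---|---|---|---|
| Visit 1 | dose 1, day 1 | 6 | 13 | dose 6, day 36 | Visit 2, 13 device doses |
| Visit 2 | dose 14, day 92 | 0 | 0 | dose 19, day 127 | Visit 3, 13 device doses |
| Visit 3 | dose 27, day 183 | 0 | 0 | dose 32, day 218 | Visit 4, 13 device doses |
| Visit 4 | dose 40, day 274 | 0 | 0 | dose 45, day 309 | Visit 5, 13 device doses |
| Visit 5 | dose 53, day 365 | 0 | 0 | dose 58, day 400 | Visit 6, 13 device doses |

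The Visit 2 row does not depend on where in its window the visit falls. After the 11th dose, Visit 2 is on day 1 + 7 × 10 + 5 = 76; after the 15th it is on day 1 + 7 × 14 + 5 = 104, each ± 1 day. The visit always lies between weekly doses and always after dose 6, so the first device dose follows both Schedule time points.

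**Can the wording be reconciled?** Note 11 uses near-identical timing words for the ex-Genotropin subjects, where the sixth dose is counted from Day 1 of the extension (Section 10.2.2.1). Its sentence on the other questionnaires for device switchers adds the transition anchor and refers to the following visit. The DUQ sentence has neither. Visit 2 is a fixed trial visit on either reading.

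**The case against.** The strongest reply is that the design itself is sound and clearly stated. The synopsis, Section 10.2.1, Section 10.2.2.4 and the Appendix 6 header all count from the device, and Section 11.7.4 says which section governs. The protocol calls the Schedule an overview. A site with a subject already past Visit 2 when the device arrives would have to turn to Section 10 and would find the right instruction there. All of this stands. A reader of the Schedule alone might infer that the protocol as a whole mistimes the DUQ; the documents do not support that.

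It could also be argued that investigational product here means the device product, since the summary of changes says the term was adopted to reflect the drug and device combination. That fails, because the same note applies the term to ex-Genotropin subjects counted from Day 1, and because it would not explain the fixed Visit 2.

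Three further limits stand:
- The DUQ is not the only information on the device. C&OS-P asks how easy the medication is to use in its current form and is correctly timed by note 11. Device logs may be read out (Section 10.2.2.5). The SAP repeats TEAEs and local tolerability for auto-injector use (Section 9.4).
- The grid gap is not peculiar to the DUQ. The C&OS-P, CSDS-P and CSDS-C rows also have no mark after Visit 2, although all three are required after a later switch.
- The DUQ sits under Other Endpoints and is summarised descriptively by question (SAP Section 11.4).

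**Conclusion.** The contradiction is real and cannot be read away, but it is confined to note 11 and the DUQ row of the Schedule. If the Schedule were followed, every subject switching at Visit 2 or later would have both DUQ time points before first device use, with 0 device doses at each. Under Section 10.2.2.4 the two time points are the sixth device dose and, nominally, 13 device doses. Only a switch at Visit 1 makes the two rules agree. This rests on weekly dosing and on the device being first used at the dose after the training visit.

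A reader might infer that most US subjects are affected, or that DUQ data will in fact be lost. The documents support neither. They show that late switching is allowed and planned for, but give no count by visit, and they do not say whether sites or the data-capture build work from the Schedule or from Section 10. The finding is a conditional risk to one descriptive endpoint. Height, IGF-1 and general safety analyses do not depend on it. Severity is minor, but the error is worth correcting because the fix is nearly free.

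**What to change.** Reword the DUQ sentence of note 11 so that the diary form is due on the day of the sixth dose given with the GH Auto-Injector, and the clinic form at the next scheduled visit after transition.

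In the grid, mark the DUQ row, and likewise the C&OS-P, CSDS-P and CSDS-C rows, with a conditional (x) at Visits 2 to 5 and later for subjects who have transitioned. Correcting the DUQ row alone would leave the same gap in the other three.

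The cost is a footnote and table correction in the next amendment or an administrative letter. No procedure, visit or sample is added.
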